3.1.2 Secondary Endpoints

3.1.2.1 Key Secondary Efficacy Endpoints

The following key secondary endpoints will be included in formal hypothesis testing procedures as described in the statistical section of this protocol.

- Length of hospital stay (time to discharge) from randomization through Day 33
- Proportion of subjects with stabilized or improved clinical status of at least one category on the 6-point clinical status scale on Day 14

- Cumulative duration of IMV from randomization through Day 33
- Proportion of subjects with severe progression defined as requiring ECMO, IMV and/or have died through Day 33
- Length of time in ICU from randomization through Day 33
- Mortality rate through Day 33

3.1.2.2 Other Secondary Efficacy Endpoints

- Results of reverse transcription polymerase chain reaction (RT-PCR) for SARS-CoV-2 from nares/throat swab and/or sputum and/or lower respiratory tract sample on Day 7.
- Proportion of subjects admitted to the ICU from randomization through Day 33
- Proportion of subjects with improvement on Days 7, 14, 21, and 33
- Proportion of subjects requiring IMV by Day 33
- Time to recovery through Day 33 where recovery is defined as a clinical status of 1 or 2
- Time to first improvement in clinical status through Day 33

3.1.2.3 Safety Endpoints

- Incidence of all AEs
- Incidence of AEs considered related to the investigational medicinal product (IMP)
- Incidence of serious adverse events (SAEs)
- Clinical laboratory parameters
- Vital sign parameters
- Radiological findings (chest CT/chest X-ray)

3.1.3 Exploratory Endpoints

- Improvement of SpO₂ on room air from Baseline (Day 1) to Day 33 using trend from all available observed data.
- Modified Borg Dyspnea Scale score at Baseline (Day 1) and on Days 7, 14, 21, and 33.
- MQoL-SIS score at Baseline (Day 1) and on Days 7, 14, 21, and 33.

3.1.4 Overall Study Design and Plan

This is a randomized, double-blind, placebo-controlled, multicenter, two-arm adaptive Phase 3 study designed to evaluate if high-dose *Octagam 10%* therapy can stabilize or improve clinical status in subjects with severe COVID-19.

Following Screening procedures, subjects that meet eligibility criteria will be randomized to receive either *Octagam 10%* in a dose of 2 g/kg over 4 days (0.5 g/kg/day), or an equivalent volume of placebo (saline). The infusion will be

administered over a period of 2 hours per day over a total of 4 consecutive days. The first dosing will take place within 24 hours of the Screening Visit.

Approximately 208 male or female adult subjects will be recruited so that approximately 104 subjects in each treatment arm will complete the study. Each subject's participation will last a total of approximately 33 days, including 29 days for safety follow-up, followed by a one-year registry follow-up.

This study is planned to start in Q2 2020 and to be completed by Q4 2020, resulting in a maximal overall duration of 7 months. The planned follow-up registry will begin in Q3 2020 and to be completed in Q4 2021.

3.2 Discussion of Study Design and Choice of Control Group(s)

3.2.1 Study Design

Given that this is an efficacy and safety study with the objective of determining if high-dose *Octagam 10%* therapy will stabilize or improve clinical status in subjects with severe COVID-19, a randomized, double-blind, placebo-controlled, multicenter study design is considered standard for this type of research (ie, the evaluation of the safety and efficacy of active versus placebo).

3.2.2 Control Group(s)

A placebo control has been chosen given the objectives of the study to determine the effects of active treatment with *Octagam 10%*. Choosing placebo as a control has a long history of being the standard for clinical investigations of new therapies for a given indication.

3.2.3 Study Parameters

Efficacy assessments include clinical status, ventilator status/means to maintain oxygen status, SARS-CoV-2 RT-PCR results, oxygen saturation, modified Borg Dyspnea Scale and MQoL-SIS. Safety assessments include AEs and SAEs, vital signs including SpO₂, clinical laboratory evaluations and CT/chest X-ray findings. The efficacy and safety assessments used in this study are consistent with those widely used, generally recognized as reliable, accurate, and relevant in this type of research, and are adequate to form the primary basis for the determination of safety and efficacy.

4 STUDY POPULATION

4.1 Population Base

Approximately 208 male or female adult subjects with laboratory-confirmed COVID-19 will be eligible for inclusion in this clinical study.

4.1.1 Inclusion Criteria

Subjects who meet all of the following criteria are eligible for the study:

1. Adult aged ≥ 18 years old.
2. Provide voluntary, fully informed written and signed consent before any study-related procedures are conducted.
3. Able to understand and comply with the relevant aspects of the study protocol.
4. Laboratory (RT-PCR) confirmed COVID-19 infection on nares/throat swab and/or sputum and/or lower respiratory tract samples at Screening or within 7 days prior to Screening.
5. Hospitalized requiring supplemental oxygen with a resting room-air SpO₂ of $\leq 93\%$ or arterial oxygen partial pressure (PaO₂)/fractional inspired oxygen (FiO₂) ratio < 300 mmHg. Measurement can be taken from documented source records in the 24 hours prior to Screening.
6. Chest imaging confirming lung involvement.

4.1.2 Exclusion Criteria

Subjects who meet any of the following criteria are *not* eligible for the study:

1. Existence of other evidence that can explain pneumonia including but not limited to: Influenza A virus, influenza B virus, bacterial pneumonia (as suggested by the combined clinical picture, radiological findings and known laboratory results [eg, elevated procalcitonin >0.5 ng/mL and concomitant neutrophilia]), known fungal pneumonia, suspected fungal pneumonia based on compromised immune system with a history of past fungal infections, noninfectious causes, etc.
2. Known history of serious allergic reactions, including anaphylaxis, to IVIG or its preparation components.
3. Subjects with a history of thromboembolic event (TEE) within the last 12 months, such as deep vein thrombosis, pulmonary embolism, myocardial infarction, ischemic stroke, transient ischemic attack, peripheral artery disease (Fontaine IV).

4. Subjects with an underlying medical condition that can lead to hypercoagulable states and hyperviscosity such as antithrombin III deficiency, Factor V Leiden, Protein C deficiency, antiphospholipid syndrome, and malignancy.
5. Known history of selective IgA deficiency with antibodies against IgA.
6. Subjects with conditions such as human immunodeficiency virus (HIV) infection, known acute or chronic hepatitis B or C (HBsAg positive or HCV RNA PCR positive or currently treated with antivirals), pulmonary fibrosis, heparin induced thrombocytopenia (HIT), and moderate to severe renal dysfunction (per investigator discretion based on estimated glomerular filtration rate [eGFR] <59 mL/min/1.73 m², as defined by KDIGO Clinical Practice Guideline):
 - Moderately reduced GFR (G3a): GFR = 45 to 59 ml/min/1.73 m²
 - Moderately reduced GFR (G3b): GFR = 30 to 44 ml/min/1.73 m²
 - Severely reduced GFR (G4): GFR = 15 to 29 ml/min/1.73 m²
 - Kidney failure (G5): GFR <15 ml/min/1.73 m².
7. Currently requiring invasive mechanical ventilation or having received invasive mechanical ventilation in the last 30 days.
8. Known clinically significant preexisting lung, heart, neuromuscular or other disease that, in the investigator's opinion, would impact the subject's ability to complete study or may confound the study results.
9. Body weight > 125kg.
10. Women who are pregnant or breast-feeding.
11. Subjects who received COVID-19 convalescent plasma, IVIG products, anti-interleukin agents (eg, Tocilizumab), or interferons for their COVID-19 disease before enrolment or plan to receive this treatment during the course of the study.
12. Enrolled in other experimental interventional studies or taking experimental medications (ie, convalescent plasma). Diagnostic studies can be allowed if the anticipated total blood volume to be drawn across both studies and for therapeutic purposes does not exceed 450 mL over any 8-week period.

4.2 Prior and Concomitant Therapy

Concomitant medication includes all pharmaceutical agents, vitamins, nutritional supplements, and herbal medicines used by the subject with the exception of *Octagam 10%* or placebo. Details on medications taken within 1 week prior to Screening and any concomitant medications taken during the study must be recorded in the electronic Case Report Form (eCRF). This includes off-label use of any drugs, devices, or interventions that have been used to manage COVID-19. Use of antivirals

(eg, remdesivir), corticosteroids, chloroquine or hydroxychloroquine, antibiotics, anticoagulants, or antiplatelet agents is allowed and must be documented in eCRF.

The use of medications being administered as part of other experimental studies or the use of experimental non-IVIG products, COVID-19 convalescent plasma, or interferons are forbidden. Should a circumstance arise where it is considered to be in the best interests of a subject to administer such a product, the subject should not receive further study infusions (*Octagam 10%* or placebo) if these are still ongoing. The other medications administered should be documented as concomitant medications, and the subject should continue to be followed up per protocol.

4.3 Withdrawal and Replacement of Subjects

4.3.1 Premature Subject Withdrawal

Subjects have the right to withdraw from the study at any time for any reason, without the need to justify their decision. The Investigator also has the right to withdraw subjects in case of AEs, poor compliance, or other reasons. Since an excessive rate of withdrawals can render the study non-interpretable, any unnecessary withdrawal of subjects should be avoided.

In addition to the ongoing safety monitoring and periodic Independent Data Monitoring Committee (IDMC) data review, the following rule will be implemented to apply temporary suspension of study drug administration, pending a safety investigation, for an unacceptable increased venous TEE or acute renal failure risk in the *Octagam 10%* group compared to the placebo group:

- For both venous TEEs or acute renal failures, the event risk will be calculated separately as (number of events reported)/(number of daily infusions) in both treatment groups, and the 90% confidence interval (CI) for the resulting risk ratio (R_{Octagam}/R_{Placebo}) will be determined by means of the / relrisk option of the SAS procedure FREQ. In case no events are observed in the placebo group, 1 will be added to each cell in the 2X2 table to enable this risk ratio evaluation. The stopping rule will be triggered if the lower confidence limit is greater than 1.0.
- This stopping rule will be applied whenever an unblinded evaluation is done, and a total of 40 daily infusions or more have been administered.
- For the first 40 daily infusions (ie, first 10 subjects that complete infusion cycle per protocol) a fixed rule will be applied by the IDMC to temporarily suspend study drug administration in case the number of related serious TEEs or acute renal failures as assessed by IDMC in the *Octagam 10%* group is triple the number in the placebo group. If no TEE or acute renal failure is observed in the

placebo group during this initial study phase, temporary suspension of study drug administration and safety investigation will be initiated if three related serious TEEs as assessed by IDMC or acute renal failures have been reported in the *Octagam 10%* group.

For any withdrawals after study entry, the Investigator will obtain all the required details and document the reason(s) for discontinuation. If the reason for withdrawal of a subject is an AE, the main specific event or laboratory test will be recorded, and the Investigator will make thorough efforts to clearly document the outcome.

Other reasons for premature termination of subjects may be:

- Withdrawal of subject's consent.
- Pregnant and lactating subjects will be immediately excluded from the study.
- Investigator's opinion that the subject may be severely harmed if he/she continues study participation, namely by the treatment and procedures requested by the study protocol.
- Occurrence of a condition or disease that interferes with the study treatment or represents an exclusion criterion.
- Administration of IVIG other than *Octagam 10%*.
- Subjects do not comply with the study protocol.

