1.2 Benefit-Risk Statement

The risks of IVIG administration are well documented. In general, the incidence of adverse events (AEs) associated with IVIG tends to increase with the rate of infusion, and thus the recommended dosage, infusion rates, and monitoring procedures should

be adhered to. Patients that are naïve to IVIG are more at risk than those that are well-maintained and on regular therapy.

Patients with pre-existing risk factors for thrombotic events (such as advanced age, obesity, hypertension, diabetes mellitus and a history of vascular disease or thrombotic episodes, patients with acquired or inherited thrombophilic disorders, patients with prolonged periods of immobilization, severely hypovolemic patients, and patients with diseases which increase blood viscosity) may be at increased risk of developing thromboembolic events (TEEs) (34). Overdose is possible in overweight and elderly patients and in those who have impaired renal function. In patients with signs of cerebral or cardiac ischemia, the increase in viscosity caused by an immunoglobulin infusion may be a risk (34).

The safety profile of *Octagam 10%* based on clinical studies and long-term post-marketing experience is well-documented and detailed in the European Summary of Product Characteristics (SmPC) (35). Adverse drug reactions (ADRs) such as chills, headache, dizziness, fever, vomiting, allergic reactions, nausea, arthralgia, low blood pressure, and moderate low back pain occur occasionally. These adverse effects are mostly transient and mild. However, some very rare adverse effects, including renal impairment, thrombosis, arrhythmia, aseptic meningitis, hemolytic anemia, and transfusion-related acute lung injury, are serious (36). AEs are rarely disabling or fatal, treatment involves supportive measures, and the majority of affected patients have a good prognosis. Reactions to IVIGs tend to be related to the dose and the rate of infusion. Rarely, human normal immunoglobulins may cause a sudden fall in blood pressure and, in isolated cases, anaphylactic shock, even when the patient has shown no hypersensitivity to previous administration. Cases of reversible aseptic meningitis and rare cases of transient cutaneous reactions have been observed with human normal immunoglobulin. Reversible hemolytic reactions have been observed in patients, especially those with blood groups A, B, and AB.

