Events that will prevent the scheduled administration of study drug will include but not limited to:

- Uncontrolled blood pressure elevation (ie, systolic is \geq 160 mmHg or diastolic is \geq 90 mmHg)
- Chest pain with or without electrocardiogram changes
- Thrombotic events
- New onset seizures

- Acute Kidney Injury (AKI) as defined by KDIGO Clinical Practice Guideline for AKI as any of the following:
 - Increase in serum creatinine by ≥ 0.3 mg/dl (≥ 26.5 $\mu\text{mol/l}$) within 48 hours
 - or Increase in serum creatinine to ≥ 1.5 times baseline, which is known or presumed to have occurred within the prior 7 days
 - or Urine volume < 0.5 ml/kg/h for 6 hours
- Stroke
- Myocardial infarction.

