8.6 Independent Data Monitoring Committee

An IDMC will be established by the Sponsor. The IDMC will be composed of recognized experts in the field who are not actively recruiting subjects.

The IDMC will review relevant data periodically during the study and will give advice on the continuation, modification, or termination of the study. A written study-specific procedure will define in detail the composition, responsibilities, and procedures of the IDMC.

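### After the first 40 infusions, the suspension rule counts venous TEEs and acute renal failures only, so an arm-level excess of arterial TEEs meets no stated boundary (minor, cheap to improve)

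*Protocol*

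**What the plan says.** Protocol 4.3.1 adds a suspension rule to ongoing safety monitoring and periodic IDMC review. Its lead-in gives the purpose: temporary suspension "for an unacceptable increased venous TEE or acute renal failure risk" in the Octagam group relative to placebo. The rule has two parts.

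- **From 40 infusions on.** "For both venous TEEs or acute renal failures, the event risk will be calculated separately" as events over daily infusions in each arm. A 90% confidence interval is formed for the risk ratio, with 1 added to each cell if placebo has no events. A lower limit above 1.0 triggers suspension. On timing: "This stopping rule will be applied whenever an unblinded evaluation is done, and a total of 40 daily infusions or more have been administered".
- **First 40 infusions.** A fixed rule applies "in case the number of related serious TEEs or acute renal failures as assessed by IDMC" in the Octagam group is triple the placebo number. If placebo has none, three such events suffice. The word venous is absent here.

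Elsewhere the protocol uses TEE more widely. Exclusion 3 refers to a "thromboembolic event (TEE) within the last 12 months, such as deep vein thrombosis, pulmonary embolism, myocardial infarction, ischemic stroke", and goes on to transient ischemic attack and severe peripheral artery disease. Section 5.4 introduces a list with "Events that will prevent the scheduled administration of study drug will include but not limited to"; the list includes thrombotic events, stroke and myocardial infarction. On IDMC procedure, Protocol 8.6 says: "A written study-specific procedure will define in detail the composition, responsibilities, and procedures of the IDMC". SAP 8 sets no boundary and refers to the charter and minutes for decision-making.

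**The concern.** At an unblinded review after infusion 40, a venous excess is tested against a stated boundary. An equal or larger arterial excess is not, because arterial events add nothing to the counts. The protocol gives no reason for the restriction, although it treats stroke and myocardial infarction as serious enough to stop dosing in the subject who has one. That hold protects a subject after the event; it compares no arms and protects nobody enrolled later. At stake is whether a harmful arterial imbalance would prompt a pause by rule or only by judgement.

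**Working it through.** **1. Which part of the rule was in force.** The protocol equates 40 infusions with 10 subjects: 10 × 4 = 40, which reproduces. SAP 8 places the first data review at about 44 subjects, that is up to 44 × 4 = 176 infusions. The venous-only part therefore applied at every review that SAP 8 describes, however TEE is read in the fixed rule.

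**2. The boundary.** I took the risk-ratio option of the SAS procedure to give the usual log-scale Wald limits. With a and b events in n1 and n2 infusions (Octagam, placebo):

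- RR = (a/n1)/(b/n2)
- SE = √(1/a − 1/n1 + 1/b − 1/n2)
- lower 90% limit = RR × exp(−1.645 × SE)

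If b = 0, then a and b each gain 1 and n1 and n2 each gain 2. Infusions are assumed equal between arms, at 88, 208 and 416 per arm (22, 52 and 104 subjects × 4).

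The fewest Octagam events that trigger against 0, 1, 2 and 3 placebo events are 5, 6, 8 and 9 at all three sizes.

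**3. Assumed counts that show the gap.** Take venous 1 vs 1 and arterial 6 vs 0, at 208 infusions per arm.

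- Venous only, 1 vs 1: SE = √(2 − 2/208) = 1.411; limit = exp(−1.645 × 1.411) = 0.098. No trigger.
- All TEEs, 7 vs 1: SE = √(1/7 + 1 − 2/208) = 1.065; limit = 7 × exp(−1.645 × 1.065) = 1.21. Trigger.

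Across the three sizes the limits are 0.098-0.099 and 1.21-1.23.

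**4. Why not simply pool.** Venous 5 vs 0 triggers (limit 1.02-1.03). Adding arterial 1 vs 2 makes the pooled count 6 vs 2, with a limit of 0.79-0.80 and no trigger. A pooled boundary in place of the venous one can hide a venous signal, so the all-TEE boundary should be added.

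**5. Operating characteristics.** The documents give no event risks. I assumed per-subject risks of 2% or 5% (venous) and 1% or 3% (arterial), four infusions per subject, and looks at 22 and 52 per arm. The first look is SAP 8's 44 subjects; the second is half of 208. Each cell is the chance of a trigger at either look, from 400,000 simulated trials, as venous only → venous or all TEEs.

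| Venous / arterial risk | No true effect | Arterial risk tripled |
|---|---|---|
| 2% / 1% | 0.15% → 0.65% | 0.16% → 4% |
| 2% / 3% | 0.16% → 2.05% | 0.16% → 24% |
| 5% / 1% | 1.9% → 3.1% | 1.9% → 7% |
| 5% / 3% | 1.8% → 4.6% | 1.9% → 23% |

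The largest relative rise in false suspensions is at 2% / 3%: 2.05/0.16 ≈ 13-fold. If the 50% review is taken as half of 176 (44 per arm), the added boundary triggers in about 3-20% of trials with tripled arterial risk.

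**The case against.** The case for leaving the rule alone has real weight.

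- **It is largely moot.** SAP 8 describes the 25% and 50% reviews in the past tense, and the one remaining meeting follows 100% of data. A suspension rule has nothing to suspend once dosing ends. This stands and is the main reason for the low severity.
- **Arterial events are not ignored.** A reader might infer that they go unmonitored. The documents do not support that. The IDMC received adverse events by arm, Protocol 8.6 lets it advise modification or termination, 5.4 holds dosing in affected subjects and Exclusion 3 removes recent cases. What is missing is only a comparative boundary. Since 4.3.1 presents its rule as additional to IDMC review, judgement alone was evidently not thought enough for venous events.
- **Section 1.2 is partial support.** It says: "In patients with signs of cerebral or cardiac ischemia, the increase in viscosity caused by an immunoglobulin infusion may be a risk". It might be read as naming ischemia as an expected effect of treatment, but there ischemia is a condition that the patient already has.
- **Exclusion 3 is not an outcome definition.** It is an open list of medical history and includes a chronic disease stage. It shows how the protocol uses the term, but it cannot be copied into a trigger unchanged.
- **The example is extreme.** Six arterial events are 6/22 = 27% or 6/52 = 12% of the Octagam arm, and an IDMC would notice. The example shows how the rule works, not a likely course.
- **Scope is a design choice.** Venous appears in both the lead-in and the confidence-interval bullet, so the restriction may be deliberate. Even so, no reason is given.

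**Conclusion.** The point holds as a minor one. Within the Protocol and SAP, no number of arterial TEEs can meet the numeric suspension boundary from infusion 40 on. It would go too far to say that no arterial trigger exists at all, because the IDMC charter was not available. Nor do the documents show that the early and later parts of the rule conflict: TEE in the fixed rule may be shorthand for venous TEE or may include arterial events.

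The gain from closing the gap is modest. If arterial risk triples, the chance of a trigger rises from about 0.2-1.9% to 4-24%, so 76-96% of such trials would still not trigger and IDMC judgement remains the main safeguard. The price is a rise in false temporary suspensions from about 0.1-1.9% to 0.6-4.6%. These figures rest on the assumed risks, the look times and equal infusions per arm. The scope gap itself rests on the text alone.

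**What to change.** In Protocol 4.3.1 and the IDMC charter:

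1. Keep the venous boundary. Add the same 90% boundary for all new-onset TEEs after first dose: deep vein thrombosis, pulmonary embolism, myocardial infarction, ischemic stroke, transient ischemic attack and acute peripheral arterial occlusion, but not chronic peripheral artery disease stage. Suspend if either lower limit exceeds 1.0.
2. State that TEE in the first-40-infusion rule covers venous and arterial events. Leave its related and serious filters and its thresholds as written.
3. Tabulate venous and arterial TEEs by arm at each unblinded review and in the study report. SAP 16 summarizes events by organ class and preferred term, which can scatter arterial TEEs over several classes.

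The cost is a wording change, one more run of the same calculation and one table. The events are already reported, so no new data are needed. The downside is the extra temporary suspensions given above. If dosing has ended, only item 3 is worth doing, at the 100% review and in the study report.
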